## **STUDY TITLE**

The Effects of Mirtogenol® with Bimatoprost on Intraocular Pressure in Hispanics with Open-Angle Glaucoma: A Double-Blind, Randomized Controlled Trial

## **RESEARCH QUESTION**

Can Mirtogenol® have an additive effect on the reduction of intraocular pressure when combined with bimatoprost in the Hispanic population with primary open-angle glaucoma?

## **HYPOTHESIS & SPECIFIC AIM**

The combination of Mirtogenol® and bimatoprost will have a superior reduction on intraocular pressure than bimatoprost with a placebo in Hispanic patients with primary open-angle glaucoma. Null hypothesis: The combination of Mirtogenol® and bimatoprost will have no difference on the reduction of intraocular pressure when compared to bimatoprost with a placebo in the Hispanic population with primary open-angle glaucoma (POAG). The specific aim of the study is to determine if the addition of Mirtogenol® to the bimatoprost 0.01% for open-angle glaucoma will have an additive effect on the intraocular pressure in the Hispanic population as compared to bimatoprost plus placebo. The continuous variable of intraocular pressure (IOP) will be compared

using a t-test to determine statistical significance. In addition, the safety of the combination of Mirtogenol® with bimatoprost will be evaluated, but no statistical analysis will be performed.

## **BACKGROUND/SIGNIFICANCE**

Glaucoma is a progressive condition caused by the degeneration and death of retinal ganglion cells and their axons that form the optic nerve, resulting in irreversible visual field reduction and blindness. Glaucoma is the second cause of legal blindness in the United States and consists of several eye disorders, the most common being open-angle glaucoma. In primary open-angle glaucoma (POAG), there is a malfunction in the ocular drainage system resulting in the accumulation of aqueous fluid that exerts pressure and may damage the optic nerves. It affects up to 4 million individuals in the United States, up to 70 million individuals worldwide and is found primarily in patients older than 50 years of age. Symptoms are not present until 25 to 35% of the nerve fibers are damaged. The American Academy of Ophthalmology states that the prevalence of POAG in Hispanics is thought to be between that of African-Caribbean and Caucasian populations. The risk of developing glaucoma increases with older age, female gender, family history of glaucoma, lower ocular perfusion pressure, lower blood pressure, thinner central cornea, optic disk hemorrhage, larger cup-to-disk ratio, and specific visual fields findings. Glaucoma is multifactorial and is affected by both intraocular pressure (IOP) dependent and non-dependent factors such as vascular damage, ocular blood flow and free radicals. Intraocular pressure can be controlled with glaucoma medications such as bimatoprost, with a successful rate between 60% to 80% of patients over a 5-year period. Progression of visual field loss still occurs in 8% to 20% of patients despite reaching standard therapy IOP goals.

Elevated intraocular pressure is considered the most significant modifiable risk factor for the development of glaucoma and ocular hypertension. The normal IOP is below 21 mmHg and the mean is around 15.5 mmHg, but POAG patients may have normal or elevated IOP reaching more than 30 mmHg. The increased IOP in all types of glaucoma may result from the decreased facility for aqueous humor outflow. The reduction of IOP at any point along the spectrum of the disease severity may reduce progression. Each 1 mm Hg in IOP reduction reduces risk of disease progression by at least 10%. The American Academy of Ophthalmology recommends the target IOP should be a 25% reduction and states that reduced risk of progression was noted with IOP consistently below 18 mmHg or largely below 14 mmHg. Prostaglandin analogs, including bimatoprost, are often recommended as first-line therapy and are considered the most potent

topical medications for reducing IOP. They work to lowering intraocular pressure by increasing both uveoscleral and trabecular aqueous humor outflow. Mirtogenol® is a potent antioxidant and free radical scavenger supplement, which has been shown to lower intraocular pressure and improve blood flow with minimal side effects. Mirtogenol® once daily oral capsule contain a synergistic combination formula of 80 mg of standardized bilberry extract, Mirtoselect® and 40 mg of the French maritime pine bark extract, Pycnogenol®.

New strategies to prevent retinal ganglion cell death are necessary, since current medications are not completely effective in halting the progression of the condition. Mirtogenol® is a supplement with antioxidant properties and free radical scavenger, which has shown to lower intraocular pressure with minimal side effects. The purpose of the study is to evaluate the efficacy and safety of the combination of Mirtogenol® and bimatoprost on intraocular pressure in POAG. Since prostaglandin analogs decrease IOP by increasing the drainage of aqueous humor, while Mirtogenol® is assumed to act on humor secretion, the combination of both may have an additive response. The objective of this study is to determine if Mirtogenol® has an additive effect on the reduction of IOP when combined with bimatoprost in the Hispanic population with primary open-angle glaucoma. To date, there have been no studies identified by the researchers in the literature review conducted, that evaluate the effect of Mirtogenol® with bimatoprost in the reduction of intraocular pressure with POAG patients in the Hispanic population. Due to current medication not being able to cure or detain POAG progression, this study may advance our knowledge on new complementary alternatives and pave the way for more studies to halt the progress of the condition in order to preserve the patient's visual function and improve quality of life.

## **LITERATURE REVIEW**

Both constituents of Mirtogenol®, Bilberry and Pycnogenol, are powerful antioxidants. The active components of Bilberry (Mirtoselect®) are flavonoid anthocyanosides (anthocyanins). Anthocyanosides are the only flavonoids able to reach the eye as a target organ in experimental animals. Unchanged anthocyanosides demonstrated after oral administration that it is absorbed and distributed into ocular tissues, showing its ability to pass through the blood-aqueous and blood retinal barriers. A meta-analysis of preliminary clinical research shows that taking bilberry anthocyanin 60 mg twice daily for at least 12 months improves visual function in patients with normal tension glaucoma when compared to pretreatment. Anthocyanins are

involved in the stabilization of collagen fibers, promotion of collagen biosynthesis, decrease capillary permeability and fragility.

Pycnogenol® major actions include antioxidant as radical scavenger, anti-inflammatory effects, and stimulation of eNOS synthesis. It has shown to improve pathologic permeability of blood vessels and has been extensively studied for enhancing capillary resistance and integrity in retinopathy. Pycnogenol® has also been found to significantly lower plasma endothelin-1, a vasoconstrictor peptide that affects the trabecular meshwork contractility, which allows for regulatory mechanisms controlling fluid outflow. Pycnogenol® has previously been shown to significantly enhance the generation of endothelial nitric oxide, involved pulsatile choroidal and total choroidal blood flow. Bilberry and Pycnogenol® may interact with immunosuppressant therapy and anticoagulant drugs. Pycnogenol® and bilberry may cause minor side effects that include gastrointestinal discomfort, dizziness, headache and nausea. Serious side-effects have never been reported for Mirtoselect® and Pycnogenol®, despite their long use in ophthalmology, predominantly for diabetic retinopathy.

Previous studies on human subjects found that Mirtogenol® alone or in combination with prostaglandin analogues can reducing IOP. A six-month study titled “Effects of Mirtogenol® on ocular blood flow and intraocular hypertension in asymptomatic subjects”, used 38 asymptomatic nonglaucoma participants with high intraocular pressure ranging from 22 to 26 mmHg. It concluded that Mirtogenol® decreased intraocular pressure from 25.2 to 22.2 mmHg and no side effects were observed. Another six-month study titled, “Mirtogenol® potentiates latanoprost in lowering intraocular pressure and improves ocular blood flow in asymptomatic subjects” evaluated the effects in three groups using Mirtogenol®, latanoprost or both with 79 asymptomatic participants with high intraocular pressure ranging from  $\geq 35$  to  $\leq 40$  mmHg without glaucoma. It concluded that the combination of both, Mirtogenol® and latanoprost, was more effective for lowering IOP from 38.0 to 24.2 mmHg and no serious side effects occurred during the study, apart from standard side effects in patients related to latanoprost. In 2017, a 12 week study titled “Mirtogenol® supplementation in association with dorzolamide-timolol or latanoprost improves the retinal microcirculation in asymptomatic patients with increased ocular pressure”, used three group with dorzolamide-timolol plus Mirtogenol®, latanoprost drops plus Mirtogenol® or latanoprost with 88 asymptomatic participants with high intraocular pressure  $> 28$  mmHg without glaucoma. It concluded that supplementation with Mirtogenol® in addition to local ophthalmic

treatments was safe and may lower IOP to normal levels and was well-tolerated without side effects.

In conclusion, we know that no data exist using Mirtogenol® on the Hispanic population, which has a high prevalence for glaucoma. No studies on the effect on stable IOP glaucoma patients and no studies have been done on a population that were already using antiglaucoma medication. Furthermore, there exist the need for data on new alternatives that may detain the progression of glaucoma. We do know that Mirtogenol® may lower intraocular pressure alone or in combination and has minimal side effects. That each 1 mm Hg in IOP reduction reduces risk of disease progression by at least 10% and progression of visual field loss still occurs in 8% to 20% of patients despite reaching standard therapy IOP goals. Our study will provide data on Hispanic population and an insight on the effects of Mirtogenol® on stable IOP in glaucoma patients. Furthermore, it will evaluate efficacy and safety of Mirtogenol® with bimatoprost 0.01% and may pave the way for more studies on new alternatives to reduce intraocular pressure and detain the progression of glaucoma.

## **METHODOLOGY AND STUDY DESIGN**

A prospective, parallel-group, double-blind, randomized placebo-controlled clinical trial will be conducted with an estimated 72 primary open-angle glaucoma patients. A double blind RCT was chosen to minimize bias and yield similar groups with the same prognostic at baseline to avoid compromising the validity of the study results. The primary efficacy endpoint of the study will be IOP and the secondary endpoint will be the safety analysis. Qualifying participants will be evaluated for inclusion and exclusion criteria by their ophthalmologist ([name]) and informed about the study objectives. If they agree to participate, relevant baseline clinical data will be collected for each participant and they will be assigned to a treatment or a control group by stratified randomization based on their age, intraocular pressure and cup-to-disk ratio. This stratified randomization will allow comparability of randomized study groups at baseline. Participants will be randomized in a 1:1 ratio to treatment group (bimatoprost 0.01% and Mirtogenol®) or control group (bimatoprost 0.01% and placebo) and be assigned a participant ID number. Once the randomization process has concluded, participants will be notified to pass by the office to receive the product and to start using the Mirtogenol® or placebo the next day. Both Mirtogenol® and placebo bottles will label drug of study and be registered with a number identification for each patient. Mirtogenol and the placebo will be stored in a destined area in the

primary investigator's pharmacy under a cool, dry environment that protects them from extreme temperature changes and light. Oral and written instructions on drug regimen, including route of administration, frequency, proper storage and mode of administer will be provided. The groups will self-instill one drop of bimatoprost 0.01% in the affected eye(s) once daily as instructed by the ophthalmologist. In addition, participants will use one (1) capsule of Mirtogenol® or one (1) placebo capsule orally daily in the morning with food. Mirtogenol® will be funded by Life Extension Clinical Research, Inc. Placebo capsules will be similar in appearance, size, and route of administration to Mirtogenol®.

The study will have five visits: screening and baseline, week 4, week 8, week 12 and week 24 of approximate 30-60 minutes of duration and an addition visit for pickup of the product after the randomization process. An ophthalmological evaluation will be conducted by a glaucoma specialist at each visit. At the baseline visit, the following tests will be performed: visual acuity, visual field evaluation, applanation tonometry, optical coherence tomography (OCT), and pachymetry. At week 4, and week 8 the following tests will be performed: visual acuity and applanation tonometry. At week 12, the following tests will be performed: visual acuity, visual field evaluation and applanation tonometry. At week 24, assessments will include the following: visual acuity, visual field evaluation, applanation tonometry, optical coherence tomography and pachymetry.

The same equipment will be used throughout the study for measurement consistency. Each test will be measured in the morning and the patient will be resting, sitting for at least 10 minutes before measurement. The tests will always be performed by the same person to rule out variations. At each visit, the IOP will be measured twice, with 10-minute intermissions between measurements, and mean values will be recorded. If only one eye is determined eligible as trial eye (meeting the diagnostic criteria for glaucoma), then all assessments will be performed only for the trial eye. If both eyes are eligible, only the eye with highest baseline mean IOP will be included in the statistical analysis. Patients will be instructed not to take any medications within two hours before measurements. Any therapy considered necessary for the patient's welfare will be given at the discretion of the treating physician and will be documented.

Safety measures include non-invasive techniques, standard of care treatment during the duration of the study, ophthalmological evaluations and assessment tests. Side effects or adverse effects will be reported and evaluated by the ophthalmologist at each visit and if deemed necessary the trial medication (Mirtogenol® or matching placebo) will be discontinued and therapy adjusted as

appropriate by the clinician. Adverse effects will be recorded at each study visit as well as the probability of possible association of the adverse effects to the treatment. Compliance will be reinforced with daily reminder for a month by email or text messages and then weekly reminders until the termination of the study. A monthly calendar will be provided to keep track of doses and possible miss doses. Patient must bring their supplement or placebo bottles and monthly track calendar to each visit and a pill count will be performed. Participants will be contacted one month after discontinuing the trial medication to assess for any prior changes or side effects.

The expected duration of the subject's participation shall be 24 weeks. The duration of the study will be one year. **Timeline:** Study January 2020- January 2021

- IRB Submission in December 2019- January 2020
- Project approval in January – January - February 2020
- Subjects recruitment process in February 2020- March 2020
- Study and data collection begin in April 2020- December 2020
- Data analysis in December 2020 – April 2021
- Final report and presentation in May 2021

## **STUDY SUBJECTS**

The data selection will be using a non-probabilistic sample with convenience sampling, preferably with a consecutive design. The individuals recruited will be Hispanic who receive services in a private ophthalmology glaucoma specialist office in San Juan, Puerto Rico.

Inclusion criteria include patients with:

1. Diagnosed with primary open-angle glaucoma (POAG)
2.  $\geq 21$  years old
3. Patient must be Hispanics (self-identified)
4. Current glaucoma treatment regimen of monotherapy with bimatoprost 0.01% administered into affected eye(s) once daily with stable IOP  $\leq$  of 21 mmHG

Exclusion criteria include patients with:

1.  $< 21$  year old,
2. Pregnant women or those who are planning to become pregnant in the next six (6) months,

3. Women who are breastfeeding,
4. Individuals with cardiovascular diseases that have required medical intervention in the past three (3) months,
5. Patients that required any kind of surgery, radiotherapy or chemotherapy in the past three (3) months,
6. Patients with advanced glaucoma with a cup to disk ratio  $> 0.9$ , previous glaucoma surgeries or other abnormalities of the eye that affect the visual pathway,
7. Patients with uveitis, diabetic retinopathy, macular edema or degenerative eye,
8. Patients with a history of adverse side effects of prostaglandin inhibitors,
9. Patients planning to undergo trabeculectomy or cataract surgery during the next six (6) months,
10. Patients using immunosuppressant therapy and anticoagulant,
11. Patients currently using Mirtogenol®.

Both bimatoprost 0.01% and Mirtogenol® have been shown to have a good tolerability profile and a low incidence of side effects in previous studies. The risks and discomfort that may result because of this study are mild and minimal. Mirtogenol® contains bilberry and Pycnogenol® which may theoretically interact with immunosuppressive therapies and anticoagulant. Mirtogenol® may cause gastrointestinal discomfort, dizziness, headache and nausea. The ophthalmic solution of bimatoprost can cause an increase in the pigmentation of the iris, periorbital tissue (eyelid) and eyelashes, conjunctival hyperemia, conjunctival edema, conjunctival hemorrhage, eye irritation, eye pain, eye itching, eyelid sprain, pruritus eyelids, blurred vision and reduced visual acuity. All visual tests will be noninvasive, but some may cause discomfort and a small chance of cornea abrasion, which usually heals in a few days.

Benefits of the study may include intraocular pressure improvement, visual examinations and tests at no cost and the results of each test performed will be provided at the end of the study. The information in this research study may lead to better treatments in the future for people with glaucoma. Safety measures include non-invasive techniques, standard of care treatment during the duration of the study, ophthalmological evaluations, and assessment tests. Side effects or adverse effects will be reported and evaluated by a specialist and discontinuation of the trial medication will occur if deemed necessary by the treating ophthalmologist. Adverse effects will be documented at each study visit and the treating ophthalmologist will assess possible association of all adverse effects to the trial

medication. A visual acuity score indicating a loss of two or more lines or a cup to disk ratio from mild ( $<0.65$ ) to moderate ( $0.7-0.85$ ) or moderate to severe ( $>0.9$ ) will be considered relevant and a possible discontinuation of the study of participant from the study. Any changes in visual field, central corneal thickness or increase in IOP will be considered relevant and will be evaluated for a possible discontinuation of the participant.

To ensure confidentiality, all information will be coded so that it cannot be associated with any individual. A separate document (code sheet) will have the participant full name and the code assigned and will be destroyed as soon as data collection has completed. The data collection form will only have the code number to avoid direct connection with the participant's personal information. All data entered into the computerized database will be identifiable by subject code number only. The individuals recruited for this study will be informed of the purpose of the investigation and treatment procedure in accordance with the Declaration of Helsinki and asked to provide written consent for their participation. All participants are required to read and sign detailed consent forms before participating in the study. Participants are advised of the voluntary nature of participation and of their right to withdraw from the project at any time and to require that information about them be removed from data analysis. Each study participant will receive a verbal and written description of the study. Contact information will include name, phone number, address, and email address of the patient and one emergency contact. All information will be kept confidential and protected under the Privacy Rule of the Health Insurance Portability and Accountability Act (HIPAA). The experimental design will be submitted to the Institutional Review Board (IRB) of the Medical Sciences Campus of the School of Medicine of Puerto Rico for approval.

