## APPENDIX

Table 1: Assessment Template

Assessment Template for Study Inclusion	
Patients Name:	
Check  with an X	
A. Inclusion criteria  Diagnosed with primary open-angle glaucoma (POAG)  Patient over 21 years old  Hispanic  Using only bimatoprost 0.01%  Consent from patient	B. Exclusion criteria include patients with:  Patient under 21 years old  Pregnant women or those who are planning to become pregnant in the next six (6) months  Women who are breastfeeding,  Cardiovascular diseases that have required medical intervention in the past three (3) months,  Patients that required any kind of surgery, radiotherapy or chemotherapy in the past three (3) months  Patients with advanced glaucoma with a cup to disk ratio > 0.9, previous glaucoma surgeries or other abnormalities of the eye that affect the visual pathway

	 Patients with uveitis, diabetic retinopathy, macular edema or degenerative eye   Patients with a history of adverse side effects of prostaglandin inhibitors   Patients planning to undergo trabeculectomy or cataract surgery during the next 6 months.   Patients using immunosuppressant therapy, and anticoagulant.   Patients who are currently using Mirtogenol®.
--	--

Table 2: Data Collection Form

Data Collection Form					
Code number: _____					
Gender	[ ] Male      [ ] Female				
Age	_____ years				
	Baseline	Week 4	Week 8	Week 12	Week 24
IOP Mean (two takes 10 min. apart)	1) _____	1) _____	1) _____	1) _____	1) _____
	2) _____	2) _____	2) _____	2) _____	2) _____

Cup to disk ratio		N/A	N/A	N/A	
Central Corneal Thickness (CCT)		N/A	N/A	N/A	
Visual acuity	____/____	____/____	____/____	____/____	____/____
Visual field changes	 Yes  No	N/A	N/A	 Yes  No	 Yes  No
Adverse Effects					

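### Exclusion 11 bars only Mirtogenol itself, so patients taking its bilberry or pine-bark components separately stay eligible; Table 1 also does not match the eligibility criteria

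*Protocol*

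**What the plan says.** **Supplement exclusion.** Exclusion 11 in Study Subjects reads "Patients currently using Mirtogenol". The checklist in Appendix Table 1 repeats it: "Patients who are currently using Mirtogenol". Both name the branded product only and current use only.

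**What the product is.** Background/Significance gives the capsule as "80 mg of standardized bilberry extract" together with "40 mg of the French maritime pine bark extract". The Literature Review then discusses the two components one at a time. It says that bilberry anthocyanosides reach ocular tissue and improve visual function. It says that the pine-bark extract lowers endothelin-1, which bears on fluid outflow, and increases nitric oxide.

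**IOP and age limits.** Inclusion criterion 4 in Study Subjects is "Current glaucoma treatment regimen of monotherapy with bimatoprost 0.01% administered into affected eye(s) once daily with stable IOP" at or below 21 mmHg, and the age limit there is 21 or older. The matching box in Table 1 is "Using only bimatoprost 0.01"%, with no mention of pressure or stability. The age boxes in Table 1 are over 21 (inclusion) and under 21 (exclusion).

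**Drug class.** Exclusion 8 is "Patients with a history of adverse side effects of prostaglandin inhibitors". Background/Significance speaks of "Prostaglandin analogs, including bimatoprost".

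**The concern.** The trial estimates what Mirtogenol adds to bimatoprost, so the control arm should be free of the product's active constituents. As written, a placebo patient can take bilberry, pine bark or both as separate supplements without breaching any stated rule, whether the use predates enrolment or begins during the 24 weeks. To the extent that such products lower IOP, the observed difference would understate the effect of Mirtogenol, and power would fall.

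The checklist problem is of another kind. Table 1 is the form for assessing inclusion, and it leaves out a criterion that defines the study population: the Literature Review presents patients with stable IOP as part of what is new in this trial. Someone working from the form alone could pass a patient whose pressure is above 21 mmHg.

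**Working it through.** **1. Is there any rule on component products?**

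- Exclusion 11 and its copy in Table 1 cover Mirtogenol only.
- Exclusion 10 concerns immunosuppressants and anticoagulants, not supplements.
- Criterion 4 asks for monotherapy, but as a description of the glaucoma treatment regimen. It names no supplement.
- Methodology and Study Design asks patients to avoid medication in the two hours before measurement and has therapy given for the patient's welfare documented. It does not address self-chosen supplements.
- The Data Collection Form (Appendix Table 2) has no entry for them.
- Limitations mentions other drugs that may affect IOP but attaches no restriction.

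The gap is therefore real, both at entry and during follow-up.

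**2. How much could it matter? An illustration.**

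Inputs from the Analytic Plan: mean IOP 15.1 mmHg, SD 3.9 mmHg, target difference 15%, 36 per group, two-sided 5% level.

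- Target difference: 0.15 × 15.1 = 2.265 mmHg. Standardised: 2.265 / 3.9 = 0.581 (the plan gives 0.60).
- Two-sided t-test power with 36 per group at 0.581: 68%. The plan states 80%. By the t-test, 80% needs 48 per group at 0.581, or 45 at 0.60. That shortfall is a separate sample-size matter and is not caused by the exclusion wording.

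Assume that a fraction c of placebo patients take a product as effective as Mirtogenol, that users in the active arm gain nothing beyond the Mirtogenol effect, and that the SD stays at 3.9. The difference becomes 2.265 × (1 − c).

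| c (assumed) | Difference, mmHg | Standardised | Power, 36 per group |
|---|---|---|---|
| 0 | 2.265 | 0.581 | 68% |
| 5% | 2.15 | 0.552 | 64% |
| 10% | 2.04 | 0.523 | 59% |
| 20% | 1.81 | 0.465 | 49% |
| 30% | 1.59 | 0.407 | 40% |

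At c = 10% the loss is 68 − 59 = 9 points. The rows show how the loss grows with c; they do not estimate what will happen.

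**3. Table 1 against Study Subjects.**

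| Item | Study Subjects | Table 1 |
|---|---|---|
| Bimatoprost 0.01% alone | required | box present |
| Stable IOP, at or below 21 mmHg | required | no box |
| Age | 21 or older | over 21; under 21 excluded |

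A patient with IOP above 21 mmHg can satisfy every box. A patient aged exactly 21 meets the criterion in Study Subjects but fits neither age box.

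**4. Drug class.** Background/Significance calls bimatoprost an analog. Exclusion 8, its copy in Table 1 and the Variables table use the term inhibitor. The Variables table applies that term to bimatoprost itself, so the class meant in exclusion 8 can be recovered from the protocol.

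**The case against.** The strongest objection concerns the dilution figures. The documents give no rate of supplement use, so every value of c is an assumption. Nor do they show that one component matches the combination: Background/Significance calls the product synergistic, and the IOP reductions in the Literature Review are all for Mirtogenol, none for bilberry or pine bark alone. If the effects of a component product and Mirtogenol simply added, use balanced across the arms by randomisation would cause no dilution. All of this stands. It limits the claim to a possible dilution of unknown size, with no directional bias expected. A reader might infer from the table that power will drop to 40%; the documents do not support that, and 12 of the 40 points between there and the planned 80% (80 − 68) belong to the separate sample-size problem.

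It can also be said that exclusion 11 is consistent wherever it appears, so widening it is a preference. In part that is so: there is no contradiction between the two lists. But the exclusion is narrower than the protocol's own account of what is active, and closing the gap costs almost nothing.

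On the checklist, a reader might infer that the trial will admit uncontrolled patients. It need not. Criterion 4 still applies, the ophthalmologist assesses the criteria, tonometry is done at baseline, and IOP is a stratification factor, so the pressure is known before allocation. Under a normal distribution with mean 15.1 and SD 3.9, about 6.5% of treated patients lie above 21 mmHg, but that is the share in an unscreened population and not a forecast of wrongly enrolled patients. The age mismatch touches only patients aged exactly 21, in a disease the protocol says is found mainly after 50.

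Finally, a reader might infer that exclusion 8 points at the wrong drugs. The Variables table rules that out; it is a naming slip.

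**Conclusion.** The point holds in a limited form. The exclusion leaves separate bilberry and pine-bark products unrestricted at entry and during follow-up, although the protocol treats both as active. The consequence is possible dilution of the treatment difference. Its size is unknown: about 9 points of power at an assumed 10% use in the placebo arm, and only if the product is fully equivalent and active-arm users gain nothing further.

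Table 1 contradicts Study Subjects on the IOP limit and on age. This opens the door to enrolment errors but leaves criterion 4 in force. The class term is inconsistent but its meaning is clear. The case for acting rests on the low cost of the correction, not on a demonstrated loss.

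**What to change.** 1. Extend exclusion 11, in Study Subjects and in Table 1, to current use of Mirtogenol or of any product containing bilberry or French maritime pine bark extract. Add an instruction to participants not to start such a product during the trial.
2. Align Table 1 with Study Subjects: add a box for stable IOP at or below 21 mmHg, and make the age box match the stated limit of 21 or older.
3. Reconcile the class term for bimatoprost across Background/Significance, exclusion 8, Table 1 and the Variables table.

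The cost is a few lines of wording, a revised one-page form and one participant instruction. At most a few candidates would be screened out. Sample size, visits and analysis are unaffected.
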